# 12.4 Data Analysis Plans

#### 12.4.1 Analysis Plans for Primary Objective

Any subjects who receive at least one dose of treatment on this protocol will be included in the analysis of the objective response rate. Patients who discontinue treatment prior to the first response assessment will be defined as "non-evaluable" but will be included in the denominator. The objective response rate and its associated 95% confidence interval will be constructed based on the exact binomial test due to the small sample size.

# 12.4.2 Analysis Plans for Secondary Objectives

Any subject who receives at least one dose of treatment on this protocol is evaluable for toxicity, progression free survival and overall survival. Toxicity rates will be summarized using frequency tables. Progression free survival and overall survival curves will be based on the Kaplan-Meier method.

Version Date: 15MAY2019 Confidential Page 53 of 60

# 12.4.3 Analysis Plans for Exploratory Objectives

To explore the relationship between specific genomic alterations with response to olaparib, Fisher's exact test will be used. To explore the relationship between prior platinum-based chemotherapy treatment (exposure, response, duration of treatment, and time since treatment) with response to olaparib, Fisher's exact test (for chemo response) and T-test (for duration of treatment and time since treatment) will be used. To explore the relationship between tumor mutational profile, circulating DNA mutational profile, and response to olaparib, both Fisher's exact test and T-test will be used.

# 12.5 Stopping Study for Excessive Toxicities

A stopping rule will be employed after 10 and 20 subjects finish at least one cycle of treatment. This safety stopping rule will be performed with respect to a) SAEs that are treatment related and b) events of specific interest (that is, MDS/AML, new primary malignancies and pneumonitis). Two-sided 95% exact binomial confidence intervals (CIs) of these event rates will be constructed at 10 and 20 subjects. If their lower bounds exceed pre-defined levels, the study drug will be considered unacceptably toxic for this patient population and the study will be terminated. Therefore, we have the following 2 stopping rules:

- 1. In a prospective trial of olaparib in subjects with advanced solid tumors and germline BRCA 1 and 2 mutations, among the ovarian, breast, pancreatic, and prostate cancer groups, 10.4%, 9.7%, 17.4%, and 12.5% of subjects, respectively, experienced serious AEs considered causally related to olaparib. We will use 15% as our cutoff and if the lower bounds of the CIs exceed 15%, the study will be halted. This corresponds to  $\geq$  5+ (5 or more) out of 10 and  $\geq$  7+ out of 20 subjects.
- 2. The rate of other events of interest (that is, MDS/AML, new primary malignancies and pneumonitis) varies around 1% (see Section 1.5.6). If the lower bounds of the CIs exceed 1%, the study will be halted. This corresponds to  $\geq$  2+ (2 or more) out of 10 and  $\geq$  2+ out of 20 subjects.

Enrollment will not be halted while these safety assessments take place.

There will be no planned interim efficacy assessment.

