Eleven of the 25 events of new primary malignancies reported by 10 olaparib-treated patients were skin cancers (2 SAEs, 9 AEs). Ten of these were the most common forms of non-melanoma skin cancer; basal cell carcinoma (n=6), squamous cell carcinoma (n=2), skin cancer (n=1) and skin neoplasm (n=1). One event of malignant melanoma was reported for a patient treated for chronic lymphocytic leukemia in an investigator-sponsored study. This patient had previously presented with a pigmented skin lesion 12 months prior to starting olaparib treatment. The lesion increased in size while on study treatment but the investigator did not consider it causally related

Version Date: 15MAY2019 Confidential Page 20 of 60

to olaparib treatment. Following surgery, the melanoma was removed and the event was reported as recovered by the investigator. The skin cancers recovered in the majority of patients.

Of the 34 patients (23 on olaparib, 11 on blinded treatment) subsequently diagnosed with a new primary malignancy, the majority of events were reported whilst on olaparib treatment. In 4 patients, the new primary malignancy was reported after the follow-up period of the study (>1 year, 68 days, 49 days and 34 days and respectively from stopping olaparib treatment). The time from start of olaparib treatment to the onset of the 36 events was <6 months for 7 patients, 6 to 12 months for 12 patients, 12 to 18 months for 2 patients, 18 to 24 months for 6 patients and >2 years for 9 patients.

There were other contributing factors/potential alternative explanations for the development of the new primary malignancy in all of the 23 olaparib-treated patients and the 11 on blinded treatment. All patients had already previously received various chemotherapy agents including multiple cycles of DNA damaging platinum containing chemotherapies, taxanes, anthracyclines and other alkylating and DNA damaging agents. Four patients were reported to have had prior radiotherapy. Twenty-five patients had a documented breast cancer gene mutation (BRCA 1 or 2). Seven patients had previous medical histories of cancer (ovarian, cervix, breast, peritoneal) prior to the cancer under investigation in the olaparib studies, and 3 patients with skin cancers had either had previous basal cell carcinoma reported or had skin lesions evident prior to study treatment.

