# 12.3 Sample Size and Accrual

Assume the null hypothesis (P0) of 10% as the response rate (the response rate with standard cytotoxic chemotherapy in this setting), a sample size of 27 achieves 81% power to detect a difference (P1-P0) of 18% (that is, P1=28%) using a one-sided exact test with a target significance level of 0.05. The actual significance level achieved by this test is 0.0471. The sample size may be inflated to 30 if replacement of subjects is needed due to early withdrawals or unevaluable subjects.

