# **13.2** Icahn School of Medicine/Tisch Cancer Institute Data Safety Monitoring Committee HCRN will provide the following for the Icahn School of Medicine/Tisch Cancer Institute's DSMC to review:

- Adverse event summary report
- Audit results if applicable
- Data related to stopping/decision rules described in study design
- Study accrual patterns
- Protocol deviations

The Icahn School of Medicine/Tisch Cancer Institute's DSMC will review study data every quarter. Documentation of DSMC reviews will be provided to sponsor-investigator and HCRN. Issues of immediate concern by the DSMC will be brought to the attention of the sponsor-investigator and other regulatory bodies as appropriate. The sponsor-investigator will work with HCRN to address the DSMC's concerns.

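### Section 12.5 gives numeric toxicity boundaries only at 10 and 20 subjects, so events in the last 7 to 10 subjects, and later events in the first 20, meet no pre-specified limit

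*Combined protocol and SAP*

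**What the plan says.** Section 12.5 (Stopping Study for Excessive Toxicities) sets two readings of the rule: "A stopping rule will be employed after 10 and 20 subjects finish at least one cycle of treatment". The method is tied to the same two points: "Two-sided 95% exact binomial confidence intervals (CIs) of these event rates will be constructed at 10 and 20 subjects". For treatment-related SAEs, "We will use 15% as our cutoff and if the lower bounds of the CIs exceed 15%, the study will be halted"; the stated counts are 5 of 10 and "7+ out of 20 subjects". For MDS/AML, new primary malignancies and pneumonitis taken together, the limit is 1% and the count is 2 at either look. Accrual is not paused for the looks.

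Section 12.3 plans 27 subjects and adds that "The sample size may be inflated to 30" if replacements are needed; the synopsis gives N = 30. The Schema continues olaparib until progression, toxicity, or the choice of patient or site investigator. Section 13.2 has the committee meet quarterly and receive, among other items, "Data related to stopping/decision rules described in study design".

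**The concern.** The rule decides whether the drug is judged unacceptably toxic in this population, yet its last numeric reading comes with 7 to 10 subjects still to be counted and with treatment of the first 20 possibly continuing. The plan's own criterion, a lower limit above 15% or 1%, can be met after that point without anything in Section 12.5 being triggered. The committee would then have to decide without an agreed threshold.

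Timing adds to this for one type of event. A subject counts towards a look after one 28-day cycle. Section 1.5.7 gives the onset of 36 new primary malignancies from the start of olaparib as "<6 months for 7 patients, 6 to 12 months for 12 patients, 12 to 18 months for 2 patients", with the other 15 later still. A rule last read when its most recent subjects may have had a single cycle is poorly matched to events with that onset.

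**Working it through.** **Inputs.** From Section 12.5: looks at 10 and 20, two-sided 95% exact intervals, limits of 15% and 1%. From Section 12.3: N = 27, up to 30. From the synopsis: accrual over an estimated 36 months.

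**Step 1: the plan's own counts.** The exact lower limit for x events in n is the 0.025 quantile of Beta(x, n - x + 1). The boundary is the smallest x whose lower limit exceeds the cutoff.

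- Related SAEs (15%): 4/10 gives 12.2% and 5/10 gives 18.7%; 6/20 gives 11.9% and 7/20 gives 15.4%.
- Events of interest (1%): 1/10 gives 0.25% and 2/10 gives 2.5%; 1/20 gives 0.13% and 2/20 gives 1.23%.

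All four stated boundaries reproduce.

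**Step 2: smallest cases that meet the criterion after the second look.**

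- Related SAEs: 6/20 continues. Four more in the next 10 gives 10/30, lower limit 17.3% (9/30 gives 14.7%). At N = 27, three more in the next 7 gives 9/27, 16.5%.
- Events of interest: 1/20 continues. Two more gives 3/30, 2.1% (2/30 gives 0.8%). At N = 27, 3/27 gives 2.35%.

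**Step 3: size of the uncovered part.** 27 - 20 = 7 subjects (26%), or 30 - 20 = 10 (33%). Assuming even accrual of 30 over 36 months, subject 20 enters at 36 × 20/30 = 24 months. With one cycle added, the second look falls near month 25, leaving about 11 months of accrual plus later treatment.

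**Step 4: the same criterion at each n from 21 to 30.**

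| Subjects counted | Related SAEs | Events of interest |
|---|---|---|
| 21-24 | 8 or more | 2 or more |
| 25-29 | 9 or more | 3 or more |
| 30 | 10 or more | 3 or more |

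**Step 5: chance of stopping.** Each subject has the event independently with probability p. The distribution of the count is carried from look to look, removing at each look the paths that cross.

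At p = 30% for related SAEs, look 1 stops 15.0% and look 2 a further 25.8%, total 40.8%. A look at 30 adds the sum, over counts k that survive look 2, of P(k at 20) × P(at least 10 - k of 10). For k = 6, 5, 4 and 3 this is 0.178 × 0.350 + 0.176 × 0.150 + 0.130 × 0.047 + 0.072 × 0.011 = 0.096, giving 50.4%.

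| Looks | SAE, p = 15% | SAE, 30% | SAE, 40% | Interest, p = 1% | Interest, 10% |
|---|---|---|---|---|---|
| 10, 20 (as written) | 2.7% | 40.8% | 76.0% | 1.7% | 60.8% |
| plus 27 | 3.1% | 49.8% | 85.2% | 1.7% | 65.2% |
| plus 30 | 3.0% | 50.4% | 86.5% | 1.8% | 68.8% |
| plus 27 and 30 | 3.3% | 52.5% | 87.6% | 1.8% | 68.8% |
| plus every n, 21-30 | 4.0% | 58% | 90% | 2.4% | 73% |

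The last row is an upper bound if p is the rate over a subject's whole follow-up: events not yet seen at a reading can only lower the count at that reading.

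**Step 6: onset data in Section 1.5.7.** New primary malignancies: 7 + 12 + 2 + 6 + 9 = 36, of which 12 + 2 + 6 + 9 = 29 (81%) began at 6 months or later. MDS/AML: duration of therapy is known for 27 patients and was under 6 months in 16; time from first dose is not given.

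**The case against.** The strongest reply is that safety is still watched after subject 20. Section 13.2 keeps quarterly review of adverse events and escalation of urgent concerns. Section 11.2.2 requires SAEs to be reported within one business day and reviewed for relatedness. Section 11.1.3 requires rapid communication of every event of special interest. Section 6.5 takes a subject off therapy for MDS/AML or pneumonitis. All of this stands. What is missing is a numeric criterion, not oversight.

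A reader might go further in three ways that the documents do not support:

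- That the rule declares olaparib acceptable if it is not crossed. Section 12.5 says only what follows from crossing.
- That late events can never count. The rule has no event window, so a late event in an early subject counts if it occurs before the 20-subject look. Only events after that look are missed.
- That MDS/AML is also shown to be a late event. The duration figures in Section 1.5.7 do not show this. Even the malignancy figures include 11 patients on blinded treatment.

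It is also fair to say that the gain is moderate: one added look still misses about half of trials with a true 30% rate. A look at full enrolment can affect ongoing treatment only, not accrual.

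**Conclusion.** The point holds as a cheap improvement to a rule whose stated counts are all correct. The numeric boundaries end at 20 subjects. After that, 7 to 10 subjects and all later events in the first 20 meet no boundary, and results such as 10/30 related SAEs or 3/30 events of interest satisfy the plan's own criterion with no rule triggered. Review continues throughout, so this is not a trial without safety monitoring.

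At a true related-SAE rate of twice the limit, the written rule stops 40.8% of the time; extending it gives about 50% with one added look and at most 58%. The gap matters most for new primary malignancies.

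The stopping probabilities assume independent subjects with a constant event probability, and that a subject's events are all known when that subject is counted. The month-25 figure assumes even accrual. The gap itself and the confidence limits need none of these assumptions.

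**What to change.** In Section 12.5, add the Step 4 table as cumulative boundaries beyond 20 subjects, with subjects counted on the same basis as at 10 and 20. State that it is read at each existing quarterly committee review while any subject is on olaparib, including after enrolment is complete. The limits, the interval and the consequence of crossing stay as the plan already has them. In Section 13.2, say that the stopping-rule data sent to the committee include these counts.

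The cost is a few lines of text, with no new meetings or data. The false-stop chance at a true 15% related-SAE rate rises from 2.7% to 3.0-3.3% with looks at 27, 30 or both, and to at most 4.0% if every n is read. For events of interest at a true 1% it rises from 1.7% to at most 2.4%.

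One limit remains. Readings that end with the last dose will not catch events long after treatment. In Section 1.5.7, 8 of the 20 MDS/AML cases with known timing came more than 60 days after stopping.

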	arrhythmia, recent (within 3 months) myocardial infarction, uncontrolled major seizure disorder, unstable spinal cord compression, superior vena cava syndrome, extensive interstitial bilateral lung disease on High Resolution Computed Tomography (HRCT) scan, history of pneumonitis, or any psychiatric disorder that prohibits obtaining informed consent.  13. Subjects unable to swallow orally administered medication and subjects with gastrointestinal disorders likely to interfere with absorption of the study medication.  14. Immunocompromised subjects, e.g., subjects who are known to be serologically positive for human immunodeficiency virus (HIV).  15. Subjects with a known hypersensitivity to olaparib or any of the excipients of the product.  16. Subjects with known active hepatitis (i.e. Hepatitis B or C) due to risk of transmitting the infection through blood or other body fluids.  17. Previous allogeneic bone marrow transplant or double umbilical cord blood transplantation (dUCBT).
TOTAL NUMBER OF SUBJECTS/ SITES	N = 30 Utilizing sites within Hoosier Cancer Research Network
ESTIMATED ENROLLMENT PERIOD	Estimated 36 months
ESTIMATED STUDY DURATION	Estimated 48 months

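### Section 12.5 applies its toxicity stopping counts only at 10 and 20 subjects and does not say what happens if a count is reached sooner

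*Combined protocol and SAP*

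**What the plan says.** Section 12.5 sets the timing: "A stopping rule will be employed after 10 and 20 subjects finish at least one cycle of treatment". The statistic is an exact interval: "Two-sided 95% exact binomial confidence intervals (CIs) of these event rates will be constructed at 10 and 20 subjects".

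- Treatment-related SAEs: "We will use 15% as our cutoff and if the lower bounds of the CIs exceed 15%, the study will be halted". The protocol gives the matching counts as "5+ (5 or more) out of 10 and" 7 or more out of 20.
- Events of special interest (MDS/AML, new primary malignancy, pneumonitis): "If the lower bounds of the CIs exceed 1%, the study will be halted". The matching counts are "2+ (2 or more) out of 10 and" again 2 or more out of 20.

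Crossing is not advisory. The drug is then considered unacceptably toxic and the study is terminated. On accrual the section adds: "Enrollment will not be halted while these safety assessments take place". It schedules no look after subject 20.

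Other sections bear on the gap between looks. Section 13.2 has the DSMC review study data every quarter, lists stopping-rule data among what it receives, and lets it raise issues of immediate concern. Section 11.2.2.1 has sites report SAEs within 1 business day, section 11.2.2.3 sends a summary to the sponsor-investigator within another, and section 11.1.3 asks for rapid communication of special-interest events. The Synopsis gives N = 30 and an enrollment period of "Estimated 36 months"; section 12.3 gives 27 before replacement.

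**The concern.** The rule is a count of affected subjects in a fixed group, and that count does not fall as more subjects are treated. Once 5 (or 2) of the subjects to be counted at the first look are affected, or 7 (or 2) of those to be counted at the second, later subjects cannot change the result of that look. Section 12.5 still evaluates nothing until the 10th or 20th subject has finished a cycle.

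Events that arrive late meet the same gap. If a second special-interest event among the first 10 subjects is reported just after the first look, the count for the second look is already reached, yet the next scheduled evaluation is about a year away at planned accrual.

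At stake is the exposure of a few more subjects to a drug that the plan's own rule would declare too toxic, with no added information for that decision.

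**Working it through.** **1. The stated counts.** The exact lower limit for x affected of n is the 2.5% quantile of Beta(x, n - x + 1).

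| Rule | Cutoff | Limit at stated count | Limit one below |
|---|---|---|---|
| Related SAE, n = 10 | 15% | 5/10: 18.7% | 4/10: 12.2% |
| Related SAE, n = 20 | 15% | 7/20: 15.4% | 6/20: 11.9% |
| Special interest, n = 10 | 1% | 2/10: 2.52% | 1/10: 0.25% |
| Special interest, n = 20 | 1% | 2/20: 1.23% | 1/20: 0.13% |

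All four counts reproduce.

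**2. Spacing of the looks.** This assumes uniform accrual, which the protocol does not state. 30/36 = 0.83 per month, so 10 subjects take 12.0 months. 27/36 = 0.75 per month, so they take 13.3 months. Accrual in one quarter is 3 x 0.75 = 2.25 to 3 x 0.83 = 2.5 subjects.

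**3. Subjects entered after the count is reached.** Illustrative assumptions: events are independent with rate p, and each is known at entry, in enrollment order. Let a and b be the counts for the first and second look.

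- First look: the a-th affected subject is subject t with probability C(t-1, a-1) p^a (1-p)^(t-a). The excess is 10 - t.
- Second look: with k < a affected at the first look and r = b - k more needed, the r-th is subject 10 + s with probability C(10, k) p^k (1-p)^(10-k) x C(s-1, r-1) p^r (1-p)^(s-r). The excess is 10 - s.
- Mean excess given a stop is the sum of excess x probability, divided by the probability of stopping.

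Worked case, special-interest events at p = 10%. First-look stop: 1 - 0.3487 - 0.3874 = 0.2639. Second-look stop: 0.3487 x 0.2639 + 0.3874 x 0.6513 = 0.3443. Total 0.608. The mean excess is 3.22 subjects before the first look and 4.77 before the second, so (0.2639 x 3.22 + 0.3443 x 4.77)/0.608 = 4.1.

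| Rule | True rate | P(stop) | Mean further subjects, given a stop |
|---|---|---|---|
| Special interest | 1% | 1.7% | 3.7 |
| | 5% | 26.4% | 3.9 |
| | 10% | 60.8% | 4.1 |
| | 20% | 93.1% | 4.5 |
| Related SAE | 15% | 2.7% | 1.5 |
| | 30% | 40.8% | 2.0 |
| | 40% | 76.0% | 2.3 |
| | 50% | 94.5% | 2.6 |

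Averaged over all trials, the excess at the plan's own rates is small: 0.017 x 3.7 = 0.06 subjects (special interest, 1%) and 0.027 x 1.5 = 0.04 (SAE, 15%).

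Largest possible excess: for special-interest events, 8 subjects before the first look (events in subjects 1 and 2) or 9 before the second (one event at the first look, then subject 11). For SAEs, 5 before the first (subjects 1 to 5) or 7 before the second (4 of 10, then subjects 11 to 13).

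**4. Does acting early change the probability of stopping?** Not if each trigger ends at its own look: a count reached before a look is still reached at that look, so the same trials stop. An open-ended trigger is different, because treatment runs to progression and events can arrive after a look. Simulation with 0.83 subjects per month, onset uniform over 0-6 months (illustrative) and 200,000 runs:

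| Case | Current rule, and trigger that lapses | Trigger without time limit |
|---|---|---|
| SAE, 15% | 1.3% | 2.7% |
| SAE, 30% | 27% | 41% |
| Special interest, 10% | 54% | 61% |

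**The case against.** The strongest reply is that the trial is not unwatched between looks. The DSMC receives stopping-rule data every quarter, SAEs and special-interest events are passed on quickly, and nothing bars action. Monitoring also follows an institutional DSMP that is not part of these documents and may contain suspension procedures. A reader might infer from section 12.5 alone that the trial must keep enrolling and dosing for up to a year after a stop is certain. The documents do not support that. What remains is that this oversight is discretionary: neither section 12.5 nor section 13.2 says whether the counts apply at the quarterly reviews. Even if they did, about 2.3 to 2.5 subjects would enter between reviews.

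A reader might also take the outcome as strictly certain once the count is reached. That goes too far. Section 12.5 refers to subjects who finish a cycle and does not say whether one who has an event and stops before then is counted. Confirmed pneumonitis requires discontinuation (sections 6.3.1 and 6.5), so the question is practical. The sponsor-investigator also assesses relatedness (section 11.2.2.3), so a count of related SAEs can fall on review.

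It is fair, too, that the excess matters mainly at event rates well above those the plan expects, and that two scheduled looks are a legitimate design. Neither point removes the case for a clarification that costs almost nothing.

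**Conclusion.** The point holds as a gap in the written rule. The counts are correct, and no contradiction or numerical error is shown. The formal rule has two looks, about 12 to 13 months apart under uniform accrual, and no provision for a count reached between them. It therefore permits entry of about 4 further subjects on average (special-interest events) or 1.5 to 2.6 (related SAEs) in trials that stop. In a trial of 27 to 30 that is worth avoiding, although at rates of 1% and 15% few trials would stop at all.

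The sizes rest on events being known at entry in enrollment order, on affected subjects belonging to the counted group, and on relatedness not being reclassified. Action between looks is possible under section 13.2; it is simply not tied to the counts.

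**What to change.** Add to section 12.5:

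- Before the first look, the rule is treated as met as soon as its n = 10 count (5 related SAE, 2 special-interest) is reached among the subjects who will be counted at that look. Between the first and second looks, the same applies to the n = 20 count (7 or 2) among those who will be counted at the second look. Each trigger lapses at its own look.
- HCRN then notifies the DSMC and the sponsor-investigator at once, and new enrollment is suspended while they confirm the count and relatedness. The existing sentence on continued enrollment stays for scheduled looks where the count has not been reached.
- A subject with a qualifying event counts even if the first cycle is not completed. The section should also say how the 10 and the 20 are identified, so that the counted group is known in advance.

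Reconcile section 13.2 with this by stating whether the DSMC applies the counts at its quarterly reviews.

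The cost is a few sentences. For a given counted group the probability of stopping, rightly or wrongly, does not change; sample size, data and visits are unaffected. The time limit is essential, because an open-ended trigger would be a stricter rule. The small downside is a possible short enrollment pause if a reported event is later reclassified.
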